18.3.2 Assent Process

For potential participants under 18 years of age, the assent of the child as well as the written informed consent of the child's legal guardian will be required for enrollment in this study. The child will receive, in language appropriate to the age and maturity of the child, an explanation of the research procedures; a description of the risks, discomforts, or inconveniences that the child might experience; and assurance that the child can withdraw from the study at any time.

The assent process will be conducted by a study staff member who is experienced in consent and assent procedures, and in accordance with IRB/IEC requirements. All study participants age < 18 years will provide oral or written assent and written consent by the participant's legal guardian, in accordance with national and/or local IRB/IEC requirements.

A participant who reaches age 18 during the study will be consented on the adult ICF at the next study visit.

18.3.3 Documenting Informed Consent

The informed consent and assent process will be documented in a narrative source note as described in the MOP.

Original, signed informed consent documents will be stored in an informed consent master binder, with a copy filed in each participant's source document binder. A third copy will be given to the participant or held separately in a secured area for the participant.

18.3.4 Stored samples

This study does not create a biobank or contribute to an existing biobank. Dried blood spots for qualitative drug levels and urine specimens will be stored on site temporarily for batched runs in Brazil and the USA.

18.4 Risks and SARS-CoV-2 Precautions

The 3HP regimen has been approved by the US FDA and is recommended by WHO for TB preventive therapy. The potential benefits of taking 3HP is a reduced risk of developing TB disease. The 3HP regimen has been found to be safe in other studies. In a recent DTG-3HP PK study, 2 of 3 participants developed a hypersensitivity syndrome. The potential harm to participants may include developing drug induced adverse reaction, particularly hypersensitivity reactions due to RPT.

1HP has demonstrated safety and tolerability during a trial in PLWH. This is the first trial of 1HP in HIV un-infected individuals.

Risks associated with study participation include the possibilities that an investigational regimen has efficacy that is inferior to the standard regimen and/or an investigational regimen is more toxic than the standard regimen, and confidentiality risks.

The following measures will minimize risk to participants: individual participants will be closely monitored clinically, and a Data and Safety Monitoring Board will review trial progress at scheduled and *ad hoc* intervals.

The investigational regimens could prove to have greater toxicity than the standard regimen. This is unlikely given that toxicity data collected in the

BRIEF TB/A5279 clinical trial showed that 1HP administered to PLWH at a once daily weight-stratified dose of rifapentine plus isoniazid for four weeks was well tolerated. However, this is the first 1HP trial to include HIV-uninfected participants.

Confidentiality risks will be minimized through the measures described in Section 18.

SARS-CoV-2 Precautions

As of July 2020, Brazil is experiencing widespread community transmission of SARS-CoV-2, the cause of COVID-19 disease. The study team will take steps necessary to protect study participants and staff from the risk of becoming infected with SARS-CoV-2 because of participation in this protocol. The study will provide personal protective equipment to the study staff, if needed.

I. Opening and closing of the protocol

- a. The trial will be opened to accrual when specific permission is obtained from local IRBs in Rio de Janeiro and Manaus, and when local and national health guidelines allow clinical research to be undertaken.
- b. The study team will suspend recruitment into the trial when advised by local and national health authorities, or when the study team determines that recruitment of participants could jeopardize the health of study staff and participants. Reopening of the trial would occur when the conditions in part I.a., above, have been met.

II. Management of enrolled participants should a shutdown be necessary.

- a. Participants receiving study medications would be advised to continue treatment until complete. Medication refills would be delivered to participants either at the study clinic or by mail.
- b. Safety monitoring would be conducted through telephone, WhatsApp, or other remote methods. Safety labs would be

collected, if possible, either by allowing participants to visit study clinics or by home visits by phlebotomists. In both circumstances strict infection control guidelines would be followed, including use of personal protective equipment by both staff and participants. If safety and monitoring labs could not be carried out, participants could continue medication with remote monitoring only, given that both study regimens are WHO-approved and known to be generally safe.

c. In the absence of SARS-CoV-2 testing it is conceivable that AEs that are due to COVID-19 could be wrongly attributed to study interventions (especially fever, nausea, and increased LFTs). In the event that a study participant developed such symptoms, study staff would facilitate access to SARS-CoV-2 testing as part of evaluating the possible AE.

18.5 Social Impact Events

Individuals enrolled in this study may experience personal problems resulting from the study participation. Such problems are termed social impact events. Although study sites will make every effort to protect participant privacy and confidentiality, it is possible that participants' involvement in the study could become known to others, and that participants may experience stigmatization or discrimination as a result of being perceived as being HIV- infected or at risk for HIV infection. For example, participants could be treated unfairly, or could have problems being accepted by their families and/or communities. Problems may also occur in circumstances in which study participation is not disclosed, such as impact on employment related to time taken for study visits.

In the event that a participant reports a social impact event, every effort will be made by study staff to provide appropriate assistance, and/or referrals to appropriate resources. Social impact events are documented and reviewed on a scheduled basis by the protocol team leadership with the goal of reducing their incidence and enhancing the ability of study staff to mitigate them when possible.

Social impact events that are judged by the IoR/designee to be serious, unexpected, or more severe or frequent than anticipated, will be reported to the responsible site's EC/IRB promptly, or otherwise in accordance with the EC/IRB's requirements.

18.6 Benefits

Both treatment regimens are offered with therapeutic warrant, meaning that it is reasonable to expect that these TPT treatments will be safe and tolerated. The study is not powered for efficacy of preventing tuberculosis. Study participants will benefit indirectly as it is well established that outcomes for participants in LTBI trials are better than those for patients receiving routine care. This study will benefit society by contributing to the understanding of optimal strategies for preventing tuberculosis.

18.7 Compensation

Participants in the study, regardless of treatment arm, will receive compensation for time and travel expenses required to attend scheduled study visits. Compensation will be in compliance with the local regulation.

18.8 Participant Privacy and Confidentiality

All participant-related information including case report forms, laboratory specimens, evaluation forms, reports, etc., will be kept strictly confidential. All records will be kept in a secure, double locked location and only research staff will have access to the records.

Participants will be identified only by means of a coded number specific to each participant. All computerized databases will identify participants by numeric codes only, and will be password-protected. Upon request, participant records will be made available to the study sponsor, the sponsor's monitoring representative, representatives of a participating pharmaceutical sponsor and applicable regulatory entities.

18.9 Certificates of Confidentiality

Certificates of Confidentiality protect the privacy interests of research participants and are limited to information that is sent to the U.S. The NIH issues Certificates of Confidentiality are part of NIH funded grant awards, such as this trial.

18.10 Critical Event Reporting

Critical event reporting is described in Section 13.

18.11 Communicable Disease Reporting

Any findings involving a communicable disease will be reported to the appropriate health authorities per Brazil's local and national requirements.

18.12 New Findings

New findings will be reported in the DSMB report, if applicable, and/or in subsequent reports, abstracts, and publications. Participants will be informed of any new findings that could affect their willingness to join the study or continue participating.

18.13 Study Discontinuation

The study may be discontinued at any time by the sponsor, investigators, DSMB, or by any of the relevant local, national, and international regulatory authorities.

18.14 Post-Trial Access

Post trial access is not applicable, because complete TPT regimens are provided in the study period.

18.15 Community Advisory Board and Other Relevant Stakeholders

The protocol will be reviewed and approved by the local institutions Research Ethics Committee (CEP) in Rio de Janeiro and Manaus and the National Health Research Commission (CONEP) and the Johns Hopkins School of Medicine (IRB).

19. ADMINISTRATIVE PROCEDURES

19.1 Protocol Registration

The study will be registered with the DMID Protocol Registration Office, if applicable.

19.2 Regulatory Oversight

The study will not operate under an IND.

19.3 Study Implementation

19.3.1 Investigator team

The investigator team of collaborators will meet at least semi-monthly by teleconference to discuss implementation progress. The meetings will be chaired by the PI.

19.3.2 Project and site implementation teams

The core project management team will oversee project implementation. The team will include the PI, Project Manager, Site Investigators, Study Coordinator, and Data Manager. The project management team will meet every 2 weeks by teleconference or face to face.

The Site implementation team will be comprised of the site investigators, clinic coordinators, and recruiters responsible for the implementation of the project at trial sites. The site implementation team will oversee the day-to-day operational aspects of the study at the trial site.

19.4 ClinicalTrials.gov

This protocol is subject to the Food and Drug Administration Amendments Act of 2007 (FDAAA) and will be registered in ClinicalTrials.gov.

20. PUBLICATION POLICY

Publication of the results of this trial will occur during the project, if appropriate, or at the end of the project, consistent with normal scientific practices. The results of the study will be submitted for publication in peer-reviewed scientific journals. Publication will occur in accordance with International Committee of Medical Journal Editors and Indian Council of Medical Research guidance, among others.

22. APPENDICES

- I Schedule of events and study duration
- II Sample study medication & food diary
- III Rifapentine hypersensitivity reaction worksheet
- **IV** List of Precautionary Medications
- V Division of AIDS (DAIDS) Table for Grading Adult and Pediatric Adverse Events, Corrected Version 2.1 (dated July 2017)
APPENDIX I Table 1A: Schedule of evaluations (SOE) for Arm A

1HP	Screening	Enrolment	On-study period*					
Study week	***	0	2	4	8	12	16	24
CLINICAL EVALUATIONS								
Informed Consent	X							
History	X	Χ						
Concomitant med list	X	Χ	Χ	Χ	Χ	Χ	Χ	Χ
TB symptom screen	X	Χ	Χ	Χ	Χ	Χ	Χ	Χ
Physical exam (complete)	X							
Physical exam (targeted)		Χ	Χ	Χ	Χ	Χ	Χ	Χ
Adverse event assessment			Χ	Χ	Χ	Χ	Χ	Χ
Adherence Questionnaire			Χ	Χ				
Pill count			Χ	Χ				
LABORATORY EVALUATIONS								
Hematology	X		Χ	Χ				
Chemistry, including LFTs	X		Χ	Χ				
Hepatitis B surface antigen (HBsAg)	X							
Pregnancy test	X	X**	Χ	Χ	Χ	Χ	Χ	Χ
HIV-1 antibody test (Documented)	X							
TB DIAGNOSTICS								
Chest x-ray	X							
TST or Interferon gamma release assay	v							
(IGRA)	Λ							
PHARMACOLOGY								
Sampling for rifapentine (dried blood			Χ	Χ				
spot)								
Sampling for isoniazid (urine)			Χ	Χ				
Sampling for NAT2 gene			Χ					
STUDY DRUG DOSING								
Isoniazid/rifapentine (once daily for 4		V	Χ	Χ				
weeks)*		Λ						
COSTING EVALUATIONS								
Patient Costing Survey (50 patients)		Χ				X		Χ
Clinic Staff Time-and-Motion****		X	X	X	X	X	X	X

*All study visits will have a visit window of +/-3 days **for individuals of childbearing potential (repeat at enrollment if screening pregnancy test was more than 48 hours prior to enrolment) *** Up to 7 days prior to enrolment **** All visits are eligible, but time-and-motion (TAM) assessments will be conducted at a randomly selected sample of study visits. The TAM assessment involves clinic staff, not study participants. † Within 90 days of screening

ЗНР	Screening	Enrolment	On-study period*						
Study week dose (dose 1 given at week 0)	***	1	2	3	8	11	16	24	
CLINICAL EVALUATIONS									
Informed Consent	X								
History	X	X							
Concomitant med list	X	X	Χ	Χ	X	Χ	Χ	Χ	
TB symptom screen	X	X	Χ	Χ	Χ	Χ	Χ	Χ	
Physical exam (complete)	X								
Physical exam (targeted)		X	Χ	Χ	Χ	Χ	Χ	Χ	
Adverse event assessment			Χ	Χ	Χ	Χ	Χ	Χ	
Adherence Questionnaire			Χ	Χ	Χ	Χ			
Pill count			Χ	Χ	Χ	Χ			
LABORATORY EVALUATIONS									
Hematology	X		Χ	Χ	Χ	Χ			
Chemistry, including LFTs	X		Χ	Χ	Χ	Χ			
Hepatitis B surface antigen (HBsAg)	X								
Pregnancy test	X	X**	Χ	Χ	Χ	Χ	Χ	Χ	
HIV-1 antibody test (Documented)	X								
TB DIAGNOSTICS									
Chest x-ray	X								
TST or Interferon gamma release assay (IGRA)	X								
PHARMACOLOGY									
Sampling for rifapentine (dried blood				X		Χ			
spot)									
Sampling for isoniazid (urine)				Χ		Χ			
NAT2 gene				Χ					
STUDY DRUG DOSING									
Isoniazid/rifapentine (once weekly for 12		v	Χ	Χ	Χ	Χ			
weeks)*		A							
COSTING EVALUATIONS									
Patient Costing Survey (50 patients)		X				Χ		Χ	
Clinic Staff Time-and-Motion****		X	X	Χ	Χ	Χ	Χ	Χ	

Table 1B: Schedule of evaluations (SOE) for Arm B

*All study visits will have a visit window of +/-3 days **for individuals of childbearing potential (repeat at enrollment if screening pregnancy test was more than 48 hours prior to enrolment) *** Up to 7 days prior to enrolment **** All visits are eligible, but time-and-motion (TAM) assessments will only be conducted at a randomly selected sample of study visits. The TAM assessment involves clinic staff, not study participants. † Within 90 days of screening

STUDY DURATION

	Yea	ar 1		Yea	ar 2		Yea	ar 3		Yea	ar 4		Yea	ar 5	
IRB aproval															
Study site preparation															
Trainning															
Enrollment															
Follow up															
Health, Economics															
and Social Data															
Collection															
Data analysis															
Manuscript															
preparation															
Final report															

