8.2 Primary Outcomes and Hypotheses

(1) Successful completion of TBT with \geq 90% adherence documented by self-report, pill count, and pharmacologic monitoring.

Hypothesis: Successful treatment with 1HP will be superior to 3HP, with 90% of individuals randomized to 1HP taking >90% of prescribed doses vs 80% of those on 3HP.

(2) Safety of treatment regimens, defined as occurrence of Grade 2 or higher targeted safety events while taking study medications or within 14 days of stopping, or discontinuation of study medications because of side effects. Targeted safety events are hypersensitivity syndrome, rash, peripheral neuropathy, hepatotoxicity, nausea and vomiting, and drug-related fever. Hypothesis: We hypothesize that the safety of 1HP will be superior to 3HP, with a rate of targeted adverse events or medication discontinuation of 6% vs. 13% for 3HP.

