9.1 Study Groups

Arm A (n=250): Experimental arm Rifapentine and isoniazid once daily for 4 weeks, 28 doses

Arm B (n=250): Control arm Rifapentine and isoniazid once weekly for 12 weeks, 12 doses

9.2 **Dosing Structure**

Dosing of rifapentine and INH will be based on the dosages given to individuals >50

kg in the BRIEF TB trial for arm A and current CDC guidelines for arm B. Based on a meta-analysis of the pharmacokinetics of rifapentine in nine clinical trials of preventive therapy conducted by Hibma and colleagues (Hibma, 2020), weightbanded dosing will not be used. This analysis demonstrated that weight-banded dosing results in sub-optimal exposures for lower weight patients, as drug clearance is not proportional to body weight. An ongoing trial of rifapentine for the treatment of active TB is currently underway and is using flat dosing of rifapentine at 1200 mg/day (TBTC Study 31/ACTG A5349) and no signals of toxicity have been reported with this dosage in lower weight individuals. In 2020, the WHO revised its guidelines for treating latent TB and recommended flat dosing of rifapentine for adolescents and adults, regardless of weight. (WHO)

Arm A Rifapentine: Isoniazid:	600 mg once daily for 4 weeks (28 doses) 300 mg once daily for 4 weeks (28 doses)
Arm B Rifapentine: Isoniazid:	900 mg once weekly for 12 weeks (12 doses) 900 mg once weekly for 12 weeks (12 doses)

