- Sampling for NAT2 gene
- urine pregnancy test for participants of childbearing potential

Week 8 (+/- 3 days)

Study team will conduct the following assessments:

- TB symptom screen
- targeted physical exam
- adverse event assessment
- adherence questionnaire
- pill count of returned HP, review of medication diary card
- CBC
- chemistry panel including liver function tests
- urine pregnancy test for participants of childbearing potential

Week 12 (+/- 3 days for visit, but not for drug sampling) Day 85 (24 hours after HP dose #12 was taken)

The participant will arrive to clinic at least an hour early, so that everything is in place for drug sampling events to begin on time.

Collect the blood and urine for drug sampling and record the exact time the sample blood and urine was collected.

The study team will conduct the following assessments:

- TB symptom screen
- targeted physical exam
- adverse event assessment
- adherence questionnaire
- patient costing survey
- pill count of returned HP, review of medication diary card
- CBC
- chemistry panel including liver function tests
- Dried blood spot and urine collection for drug sampling
- urine pregnancy test for participants of childbearing potential

This is the final dose for the 3HP regimen.

Week 16 (+/- 3 days)

The study team will conduct the following assessments:

- TB symptom screen
- targeted physical exam
- adverse event assessment

- urine pregnancy test for participants of childbearing potential

Week 24 (+/- 3 days)

The study team will conduct the following assessments:

- TB symptom screen
- targeted physical exam
- adverse event assessment
- urine pregnancy test for participants of childbearing potential
- patient costing survey

This is the final study visit.

12.1.5 Treatment completion and successful treatment.

1HP

Completion of therapy is defined as having completed 28 daily doses of treatment within 6 weeks. Treatment success is defined as having taken at least 25 doses of medication confirmed by patient report and pill count, and having rifapentine or isoniazid detected in urine or DBS specimens.

3HP

Completion of therapy is defined as having completed at least 12 weekly doses of treatment within 18 weeks. Treatment success is defined as having taken at least 11 doses of medication confirmed by patient report and pill count, and having rifapentine or isoniazid detected in urine and DBS specimens.

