13.2 Adverse Event Procedures and Reporting Requirements

13.2.1 Adverse Events

An adverse event is any untoward medical occurrence in a patient or clinical investigation subject administered a study agent and which does not necessarily have a causal relationship with the treatment received.

All Grade 2 or higher clinical or laboratory adverse events will be captured.

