15.8.3 Analysis Plan

Analyses will be intention-to-treat for both primary outcomes of successful completion and safety. For the successful completion outcome, losses to follow up (at 4 weeks for Arm 1HP and 12 weeks for Arm 3HP) will be considered as unsuccessful; a sensitivity analysis will be conducted among those not lost in both arms as of 12 weeks. For the safety outcome as of 24 weeks, losses will be considered as failures (safety events).

For the primary outcomes, if fewer than 5% of failures occur in households with 2 or more failures, p-values will be calculated using Fisher's exact test, and 95% confidence intervals (CI) for risk differences will be calculated using the standard asymptotic formula.

Otherwise, within-household correlation will be accounted for using

generalized estimating equations with logit link (for p-value) or identity link (for risk difference CI) and exchangeable correlation structure. If there are convergence problems, a log link function will be used, with delta-method-constructed confidence intervals.

Incidence of active tuberculosis will only be assessed during six months following enrollment but will be evaluated as an exploratory outcome. Incidence will be compared using Kaplan-Meier estimates at 24 weeks and Greenwood's variance formula. This will be a sufficiently rare event that within-household correlation will be ignorable. Censoring will be at last study visit or death. As a sensitivity analysis, TB-free survival will also be analyzed.

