10.3.1 Treatment Success and Safety

A superiority framework will be used for these analyses, with statistical significance defined as p<0.05 for each of the two primary outcomes. No multiplicity correction will be employed.

For each of the primary outcomes, if fewer than 5% of failures (unsuccessful treatment; specified Grade 2 event) occur in households with 2 or more failures, p-values will be calculated using Fisher's exact test, and 95% confidence intervals (CI) for risk differences will be calculated using the standard asymptotic formula.

Otherwise, within-household correlation will be accounted for using generalized estimating equations with logit link (for p-value) or identity link (for risk difference CI) and exchangeable correlation structure. If there are convergence problems with the risk difference estimation, a log link function will be used, with delta-method-constructed confidence intervals for risk differences.

Subgroup analyses will be performed by:

Site Sex Age (dichotomized at overall median) Weight (dichotomized at overall median)

Interaction tests will assess differential effects.

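### Scheduled liver tests stop at week 4 in 1HP and at week 11/12 in 3HP, but the SAP counts the safety outcome to 24 weeks in both arms, so silent laboratory hepatotoxicity is unequally ascertained

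*Protocol*

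**What the plan says.** **Schedule.** Protocol 9.1 defines the arms as "Rifapentine and isoniazid once daily for 4 weeks, 28 doses" and "Rifapentine and isoniazid once weekly for 12 weeks, 12 doses". The visit lists in Protocol 12.1.4 include a "chemistry panel including liver function tests" at weeks 2 and 4 in Arm A, and at weeks 2, 3, 8 and 12 in Arm B. Appendix I shows the same counts under "Chemistry, including LFTs", with the last Arm B draw at week 11. The blood-volume table in 12.2.2 places the second Arm B draw at week 4. Neither arm has a routine draw at weeks 16 or 24. Clinical adverse event assessment takes place at six post-enrolment visits in each arm. Protocol 6.2.1 provides for liver tests prompted by symptoms, in both arms, during and after treatment.

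**Outcome.** Hepatotoxicity is one of six targeted events, and discontinuation for side effects also counts. Protocol 13.2.1 states: "All Grade 2 or higher clinical or laboratory adverse events will be captured". SAP 10.3.1 states: "A superiority framework will be used for these analyses".

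**Window.** Protocol 6 and 8.2 restrict targeted events to those occurring "while taking study medications or within 14 days of stopping". Protocol 15.8.3 has no such limit and says: "For the safety outcome as of 24 weeks, losses will be considered as failures (safety events". SAP 10.2.2 also takes the outcome as of 24 weeks, and SAP 7 uses data collected through 24 weeks.

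Neither document mentions the unequal laboratory schedule or plans an analysis that addresses it.

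**The concern.** A silent Grade 2 or higher liver abnormality is found only when blood is drawn. Without symptoms, that means a scheduled draw. The scheduled draws follow treatment length and stop when it ends, while the outcome continues to week 24 in both arms. From about week 5 to week 12, 3HP participants are still being tested and 1HP participants are not. A rise from an unrelated cause in that period can make a 3HP participant a safety failure and pass unnoticed in a 1HP participant.

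The trial tests superiority of 1HP on safety at p<0.05. If the primary composite favours 1HP, the planned analyses cannot show how much of the difference comes from the regimens and how much from the testing schedule.

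**Working it through.** **1. Draw counts, checked against a stated figure.** The blood-volume totals in Protocol 12.2.2 reproduce only with two and four on-study draws:
- 1HP: 14 + 5 + 5 = 24 ml, as stated.
- 3HP: 14 + 4.5 + 5 + 4.5 + 5 = 33 ml, as stated.

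**2. Testing density.**

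| | 1HP | 3HP |
|---|---|---|
| Scheduled on-study draws | 2 | 4 |
| Per treatment week | 2/4 = 0.50 | 4/12 = 0.33 |
| Per week of treatment plus 14 days | 2/6 = 0.33 | 4/14 = 0.29 |
| Per week over 24 weeks | 2/24 = 0.083 | 4/24 = 0.167 |

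1HP is tested more densely on treatment. 3HP is tested more densely over the 24 weeks of the outcome.

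**3. Background or transient findings.** Assume that each draw has the same probability q of showing a silent Grade 2 or higher value, independently, in either arm. The probability of at least one finding in k draws is 1 − (1 − q)^k. The documents give no value for q. Protocol 11.1.2 gives only an any-grade rate of asymptomatic elevation on isoniazid (10–20%), so a range is shown.

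| q | 2 draws | 4 draws | Gap (points) |
|---|---|---|---|
| 0.5% | 1.00% | 1.99% | 0.99 |
| 1% | 1.99% | 3.94% | 1.95 |
| 2% | 3.96% | 7.76% | 3.80 |

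The hypothesised difference is 13% − 6% = 7 points.

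**4. Effect on the test.** Suppose both arms have a true 6% risk from all other causes. The composite risk is then 1 − 0.94 × (1 − q)^k. With 250 per arm, the chance of a significant result favouring 1HP is Φ{[d√250 − 1.96√(2p̄(1 − p̄))] / √[p₁(1 − p₁) + p₃(1 − p₃)]}, where p₁ and p₃ are the 1HP and 3HP risks, p̄ is their mean and d = p₃ − p₁. Household clustering is ignored. With no gap the chance is 2.5%.

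| q | 1HP | 3HP | Gap (points) | Chance of significance favouring 1HP |
|---|---|---|---|---|
| 0.25% | 6.47% | 6.94% | 0.5 | 4% |
| 0.5% | 6.94% | 7.87% | 0.9 | 6% |
| 1% | 7.87% | 9.70% | 1.8 | 11% |
| 2% | 9.72% | 13.30% | 3.6 | 24% |

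**5. Episodes that last.** Now assume that a silent episode lasts D weeks (1 to 4, assumed) and starts at a uniformly distributed time in the window. It is found if a scheduled draw falls inside it. For D = 2:
- On treatment, 1HP: the draws at weeks 2 and 4 cover onsets in weeks 0–4, so 4/4 = 100%.
- On treatment, 3HP: the Appendix I draws cover 3 + 2 + 2 = 7 of 12 weeks, or 58%. With draws at weeks 2, 4, 8 and 12 it is 8/12 = 67%.
- Onset anywhere in 24 weeks: 4/24 = 17% for 1HP, and 7/24 to 8/24 = 29–33% for 3HP.

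Over D = 1 to 4 and the three versions of the Arm B draw times, the 3HP:1HP ratio of detection probability is:
- 0.58 to 1.00 on treatment only;
- 0.75 to 1.29 for treatment plus 14 days;
- 1.75 to 3.0 over 24 weeks.

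The event window thus decides the direction.

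**The case against.** The strongest reply is that draws follow exposure. 3HP is given for three times as long, and its draws at weeks 8 and 11/12 fall while participants are still being dosed. A Grade 2 rise found then may be real toxicity of a longer regimen, which the trial is meant to compare. If silent episodes began at the same weekly rate on treatment in both arms, 3HP would show 1.75 to 3.0 times as many detected episodes, simply because it has more weeks at risk. Those would be genuine events. This stands, and it is why the affected events should not be removed from the primary analysis.

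Three stronger readings are tempting, but the documents do not support them.
- A reader might infer that a silent event has twice the chance of detection in 3HP. Twice as many draws is not twice the detection probability. In the independent-draw model the ratio is 1 + (1 − q)², which is always below 2 (1.99 to 1.96 for q of 0.5% to 2%, 1.64 at 20%). It moves toward 1 when an elevation persists across draws. For on-treatment episodes it is often below 1.
- A reader might hold the lack of a scheduled test in the 14 days after the last dose against 1HP alone. That gap is the same in 3HP.
- A reader might treat every extra 3HP finding as spurious. That follows from the equal-probability assumption in step 3 of the working, not from anything in the plan.

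The scope is also narrow. It covers laboratory-only events within one of six targeted components, plus any discontinuations that such events trigger.

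**Conclusion.** The concern holds in this limited form. The counts of two and four draws are certain, and so is the absence of any planned analysis that addresses them. With the outcome counted to 24 weeks, silent laboratory hepatotoxicity arising between about week 5 and week 12 can be found by a scheduled test only in 3HP. For background or transient findings this leans the composite toward 1HP.

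The size cannot be fixed from the documents, which give no rate, timing or duration for silent Grade 2 or higher elevations. The illustrative gaps of about 1.0, 2.0 and 3.8 points rest on assumed per-draw rates, equal between arms and independent between draws. For episodes arising on treatment, the direction may reverse. Part of any excess in 3HP may be true regimen toxicity. The present analysis cannot separate these explanations, and a low-cost addition would help a reader to judge them.

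**What to change.** 1. Reconcile the event window. Protocol 6 and 8.2 (on treatment or within 14 days of stopping) and Protocol 15.8.3 with SAP 10.2.2 (24 weeks) should state one definition for the primary safety outcome.
2. Add to SAP 10.3.1 a pre-specified sensitivity analysis of the 24-week composite that excludes events first found only on a scheduled draw in a participant without symptoms. Run it with and without discontinuations triggered solely by such a draw. This matters because Protocol 14.2.5 includes a laboratory stopping criterion that applies regardless of symptoms, and discontinuation is itself part of the composite. Report laboratory hepatotoxicity by draw and by arm.
3. Show this analysis beside the primary result wherever safety superiority is claimed.

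The 24-week basis is deliberate. Over 24 weeks both arms have six scheduled clinical assessments. Within treatment plus 14 days, 1HP has two (weeks 2 and 4) and 3HP has four, so a symptom-based analysis in that window would keep an imbalance of its own.

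The cost is a little extra analysis of events the trial already captures, provided that the record shows how each event was first found and whether symptoms were present. No extra blood test or visit is needed. The downside is that the analysis drops some real asymptomatic hepatotoxicity, and liver injury in HIV-uninfected people is central to the safety rationale in Protocol 7.2. It should therefore remain a sensitivity analysis and not replace the primary.
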